6.2. Respondent withdrawal

Respondents can decline to participate or stop taking the survey at any time. Only completed surveys that include all questions answered that were required to be presented for participation will be included in the analysis.

Respondents will be informed when they access the survey that they may be contacted if there are any questions about their survey responses. Respondents will be informed that their answers to the survey questions will not affect their ability to receive Humalog U-200 KwikPen.

6.3. Central Institutional Review Board (IRB)

This protocol was reviewed and approved by a central IRB before administration of the survey.

7. MANAGEMENT AND REPORTING OF ADVERSE EVENTS/ADVERSE REACTIONS

This study does not involve data collection on clinical endpoints on individual respondents.

The Internet survey does not include questions that could potentially identify a safety event, nor does it provide a free text field where study participants could specify information that may constitute a safety event (defined as an adverse event, product complaint, or other reports; e.g. overdose, abuse, misuse, off label use, pregnancy exposures, breast feeding exposures, lack of drug effect, medication error and suspected transmission of infectious disease). Free text fields are available in the survey to only collect contact information to provide payment. However, it is possible that while in conversation with UBC Personnel, a telephone respondent may provide information that could constitute a Safety Event.

Trained UBC Personnel will record any reference to a Safety Event in temporal association with Humalog U-200 KwikPen as stated (verbatim) in the UBC Humalog U-200 KwikPen Safety Event Form, along with the respondent's contact information, if consent to provide contact information is given. The respondent will also be informed that someone from Lilly may contact them to obtain additional information about the event. If consent is not granted, UBC personnel will report the Safety Event with the information provided by the respondent. Information on all reports that may constitute a Safety Event will be forwarded to Lilly as described in the Safety Event Reporting Procedure (SERP). Additional detail regarding processes for adverse event reporting will be specified in the SERP. Study personnel are requested to report suspected adverse reactions with Lilly drugs not under evaluation and with any non-Lilly drugs to one appropriate party to avoid duplication, (for example, regulators or Lilly) as they would in normal practice as required by applicable laws, regulations and practices.

8. PLANS FOR DISSEMINATING AND COMMUNICATING STUDY RESULTS

A final report for each stakeholder group describing the survey objectives, detailed methods, results, discussion, and conclusions will be developed at the end of the survey.

ANNEX 1. LIST OF STAND-ALONE DOCUMENTS

Number	Document reference number	Date	Title
1	Appendix I.1		HCP Survey
2	Appendix I.2		Survey Invitation letter for HCPs
3	Appendix I.3		Patient Survey
4	Appendix I.4		Survey Invitation letter for Patients
5	Appendix I.5		Direct Healthcare Professional Communication on the correct use of Humalog KwikPen®, 200 units/mL (Humalog® U-200 KwikPen®)
6	Appendix I.6		Patient Information Letter/ IMPORTANT SAFETY INFORMATION for Humalog® U-200 KwikPen® (insulin lispro)

APPENDIX I.1 HEALTHCARE PROFESSIONAL SURVEY

SURVEY LEGEND

- **[PROGRAMMER]** is used to indicate directions to the programmer and is set in bold, red, uppercase letters between square brackets.
- **(INTERVIEWER)** is used to indicate directions to the telephone interviewer and is set in bold, blue, text between parentheses. This text appears when content is to be administered by telephone only (for example, spontaneous AE reporting).
- **[ONLINE]** indicates a question is worded specifically for administering the survey online.
- **[TELEPHONE]** indicates a question/section is worded specifically for administering the survey over the telephone.
- **[BEGIN SURVEY CONTENT]** and **[END SURVEY CONTENT]** are used to indicate to the programmer the type of survey administration and the beginning and end of the survey or sections within the survey content.

- **[TERMINATE]** is displayed next to responses that should cause the survey to end. The following termination language will be programmed into the survey or read by the interviewer.

Thank you very much for your time today. Based on your answer, you are not eligible to take this survey. We appreciate your interest in the survey.

- **[RANDOMIZE LIST]** is inserted before questions to indicate to the programmer that the responses should be randomized. Responses such as “I don’t know,” “Prefer not to answer” or “None of the above” will always appear at the end of the randomized responses.
- **[GO TO Qx]** (skip logic) is inserted after a response to indicate to the programmer that the survey should skip to the indicated question (for example, **[GO TO Q17]** skips to question 17). If no skip logic is indicated the survey continues to the next question in the sequence.
- **[MULTILINE INPUT]** indicates to the programmer that multiple lines should be provided for data entry (for example, two address lines).
- **[FREE TEXT]** indicates to the programmer that one line should be provided for data entry.

SURVEY LEGEND

- **[DROP-DOWN LIST INPUT WITH STATES TABLE]** indicates to the programmer that the response should be a drop-down list containing the states in the table below.

Alabama	Georgia	Massachusetts	New York	Tennessee
Alaska	Hawaii	Michigan	North Carolina	Texas
Arizona	Idaho	Minnesota	North Dakota	Utah
Arkansas	Illinois	Mississippi	Ohio	Vermont
California	Indiana	Missouri	Oklahoma	Virginia
Colorado	Iowa	Montana	Oregon	Washington
Connecticut	Kansas	Nebraska	Pennsylvania	West Virginia
Delaware	Kentucky	Nevada	Rhode Island	Wisconsin
District of Columbia	Louisiana	New Hampshire	South Carolina	Wyoming
Florida	Maine	New Jersey	South Dakota	
	Maryland	New Mexico		

- The following is used to categorize survey populations into standard geographic regions but it is not displayed in the survey.

Geographic Distribution (based on address)¹: Northeast, Midwest, South, and West regions

Northeast Region

- New England Division - ME, NH, VT, MA, RI, CT
- Middle Atlantic Division - NY, NJ, PA

Midwest Region

- East North Central Division - OH, IN, IL, MI, WI
- West North Central Division - MN, IA, MO, ND, SD, NE, KS

South Region

- South Atlantic Division - DE, MD, DC, VA, WV, NC, SC, GA, FL
- East South Central Division - KY, TN, AL, MS
- West South Central Division - AR, LA, OK, TX

West Region

- Mountain Division - MT, ID, WY, CO, NM, AZ, UT, NV
- Pacific Division - WA, OR, CA, AK, HI

¹ U.S. Census Bureau, last revised Friday, 27-Jul-2001 12:59:43 EDT.

[BEGIN WELCOME PAGE]

This survey should take approximately 15 minutes to complete. If you cannot complete the survey at this time, please return when you can. Once you begin the survey you will need to answer all questions; you will not be able to access the survey again if you exit.

Consider the following important information before you start the survey: the application will time out after 30 minutes of inactivity. If your session times out, you will not be able to log back into the survey to complete it and your participation in the survey will end.

If you are ready to begin the survey at this time, please click Continue. If not, click Return Later and return to this site when it is convenient for you.

Please note: Do not use the browser's back button during this survey.

[END WELCOME PAGE]

[PROGRAMMER, DISPLAY THE FOLLOWING IN THE SURVEY PAGE HEADER: If you have questions or problems with the survey, please contact the Survey Coordinating Center at [name].]

[BEGIN SCREENING QUESTIONS]

Please provide a response to all questions and statements as they are presented.

1. Do you agree to take part in this survey about Humalog® 200 units/mL KwikPen® (Humalog® U-200 KwikPen®)?
 - Yes
 - No **[TERMINATE]**

[Q2 - FOR WAVE 2 ONLY]

2. Have you ever participated in this survey for Humalog® U-200 KwikPen® before?
 - Yes **[TERMINATE]**
 - No
 - I don't know **[TERMINATE]**

3. In which state or territory do you practice and are you licensed?

[DROP DOWN LIST INPUT WITH STATES TABLE, EXCLUDE PREFER NOT TO ANSWER]

[IF RESPONDENT ANSWERS MASSACHUSETTS, MINNESOTA, VERMONT, OR DISTRICT OF COLUMBIA, DISPLAY REMINDER MESSAGE 1 ON SAME PAGE AND GO TO Q4.]

[REMINDER MESSAGE 1]: If you practice and you are licensed in the District of Columbia, Massachusetts, Minnesota, or Vermont just a reminder that we appreciate your participation; however, no compensation for your services will be provided in accordance with local laws.

4. Please choose an option about your participation in this survey.
 - i. ○ I will participate in the survey and provide my contact information.
 - ii. ○ I will participate in the survey but choose not to be paid.

5. Are you involved in the management of patients with diabetes? This includes prescribing medications to treat diabetes or providing education to help manage diabetes.
- Yes
 - No **[GO TO Q7, TERMINATE AFTER Q14]**
6. What is your role in the management of patients with diabetes?
- Physician
 - Nurse Practitioner
 - Physician Assistant
 - Registered Nurse **[GO TO Q8]**
 - Other **[GO TO Q8]**
7. What is your primary medical specialty?
- General Internal Medicine
 - Endocrinology/Diabetology
 - Family Medicine
 - Other
8. How many years have you been in practice as a physician, physician assistant, or nurse since completing your medical/nursing education?
- Less than 5 years
 - 5 – 10 years
 - 11 – 15 years
 - More than 15 years

9. In what type of facility do you work?
- General Practice
 - Hospital
 - Other
10. Are you aware of the insulin product Humalog® U-200 KwikPen®?
- Yes
 - No **[GO TO Q12, TERMINATE AFTER Q14]**
 - I don't know **[GO TO Q12, TERMINATE AFTER Q14]**
11. For how many patients have you prescribed, or managed their treatment with, Humalog® U-200 KwikPen®?
- 0 **[TERMINATE AFTER QUESTION 14 IF 140 OR MORE COMPLETE RESPONDENTS HAVE ANSWERED 0, WHERE 140 IS A CONFIGURABLE NUMBER]**
 - 1 – 5
 - 6 – 10
 - 11 – 20
 - More than 20

12. Have you or any of your immediate family members ever worked for Eli Lilly and Company (Lilly), United BioSource Corporation (UBC), or the Food and Drug Administration (FDA)?

- Yes **[TERMINATE AFTER QUESTION 14]**
- No
- I don't know **[TERMINATE AFTER QUESTION 14]**

13. Which of the following groups best describes your age?

- Less than 30
- 30 – 39
- 40 – 49
- 50 – 59
- 60 – 69
- 70 or older

14. What is your gender?

- Male
- Female

[END SCREENING QUESTIONS]

[BEGIN SURVEY CONTENT]

[BEGIN PREAMBLE 2 – DISPLAY ON SAME PAGE AS NEXT QUESTION]

The following questions are about Humalog® U-200 KwikPen®.

[END PREAMBLE 2]

15. Please answer True, False, or I don't know for each of the following statements regarding Humalog® U-200 KwikPen®.

	[RANDOMIZE LIST]	True	False	I don't know
A	Humalog® U-200 KwikPen® is approved for transfer to syringe or pump.			
B	The dose of insulin does not need to be converted when changing patients from one Humalog strength to the other (for example, changing a patient from Humalog U-100 units/mL to Humalog® U-200 KwikPen®).			
C	When prescribing Humalog® U-200 KwikPen®, it is important to clearly indicate the correct strength on the prescription.			
D	It is important to instruct your patients that they should always have a backup pen available.			

16. Are you aware of the Direct Healthcare Professional Communication provided to you by Eli Lilly and Company on the correct use of Humalog® U-200 KwikPen® (*insulin lispro*) to minimize medication errors?

- Yes
- No **[GO TO Q18]**
- I don't know **[GO TO Q18]**

17. Did you read the Direct Healthcare Professional Communication provided to you by Eli Lilly and Company on the correct use of Humalog® U-200 KwikPen® (*insulin lispro*) to minimize medication errors?
- Yes
 - No
 - I don't know
18. Are you aware of the patient communication Patient Information Letter/*IMPORTANT SAFETY INFORMATION FOR* Humalog® U-200 KwikPen® (*insulin lispro*) that is included in patient sample packs of Humalog® KwikPen® provided by Eli Lilly and Company?
- Yes
 - No **[GO TO Q20]**
 - I don't know **[GO TO Q20]**
19. Have you read the patient communication: Patient Information Letter/*IMPORTANT SAFETY INFORMATION FOR* Humalog® U-200 KwikPen® (*insulin lispro*) provided by Eli Lilly and Company?
- Yes
 - No
 - I don't know

[DO NOT DISPLAY QUESTION 20 IF 0 IS SELECTED IN QUESTION 11]

20. Do you or another healthcare professional at your practice discuss the safe use of the Humalog® U-200 KwikPen® to patients receiving their initial prescription?
- Yes
 - No
 - I don't know

[DO NOT DISPLAY QUESTION 21 IF 0 IS SELECTED IN QUESTION 11]

21. Do you or another healthcare professional at your practice discuss the Patient Information Letter/*IMPORTANT SAFETY INFORMATION FOR* Humalog® U-200 KwikPen® (*insulin lispro*) with patients at the time of initial prescription of Humalog® U-200 KwikPen®?
- Yes
 - No
 - I don't know

[TELEPHONE: BEGIN SAFETY EVENT – KEEP ON ONE PAGE]

(INTERVIEWER: Please record if respondent spontaneously reported a safety event or product complaint during the course of this interview.)

- Yes
- No

Enter Safety Event or Product Complaint Verbatim

[MULTILINE INPUT]

(INTERVIEWER: Indicate to the respondent that someone may call back to ask more questions about the adverse event or product complaint that was reported.)

[TELEPHONE: END SAFETY EVENT]

[BEGIN CLOSING 1]

[DISPLAY CLOSING 1 IF QUESTION 4= i.]

We would like to send you \$100 as compensation for your time and effort as well as a copy of the Dear Healthcare Professional Communication (DHPC) for Humalog® U-200 KwikPen®, and the correct answers to key safety message questions, but need your name and address to do so. Do you agree to provide your contact information for this purpose?

- Yes **[IF SELECTED, DISPLAY CONTACT INFORMATION ON SAME PAGE]**
- No **[GO TO CLOSING 3]**

[END CLOSING 1]

[BEGIN CLOSING 2]

[DISPLAY CLOSING 2 IF QUESTION 3= MASSACHUSETTS, MINNESOTA, DISTRICT OF COLUMBIA OR VERMONT OR QUESTION 4 = ii OR IF NO TO CLOSING 1.]

Do you agree to give us your name and mailing address so we can send you a copy of the Dear Healthcare Professional Communication (DHPC) for Humalog® U-200 KwikPen®, as well as the correct answers to key safety message questions?

- Yes **[IF SELECTED, DISPLAY CONTACT INFORMATION ON SAME PAGE]**
- No **[GO TO CLOSING 3]**

[END CLOSING 2]

[BEGIN CONTACT INFORMATION]

FIRST NAME: **[FREE TEXT]**

LAST NAME: **[FREE TEXT]**

MIDDLE INITIAL: **[OPTIONAL; MUST BE 1 ALPHA CHARACTER]**

ADDRESS: **[MULTILINE INPUT]**

CITY: **[FREE TEXT]**

STATE: **[DROP-DOWN LIST INPUT WITH STATES TABLE]**

ZIP CODE: **[MUST BE 5-DIGIT NUMERIC ONLY]**

[END CONTACT INFORMATION]

[BEGIN CLOSING 3]

This completes the survey. Thank you again for your participation.

[END CLOSING 3]

[END SURVEY CONTENT]

HEALTHCARE PROFESSIONAL CORRECT ANSWER DOCUMENT

**Correct Responses to PRESCRIBER Survey Questions about
Key Safety Messages for Humalog® U-200 KwikPen®**

Q: Please answer True, False, or I don't know for each of the following statements regarding Humalog® U-200 KwikPen®.

STATEMENT	Correct Response
Humalog® U-200 KwikPen® is approved for transfer to syringe or pump.	FALSE
The dose of insulin does not need to be converted when changing patients from one Humalog strength to the other (for example, changing a patient from Humalog U-100 units/ml to Humalog® U-200 KwikPen®).	TRUE
When prescribing Humalog® U-200 KwikPen®, it is important to clearly indicate the correct strength on the prescription.	TRUE
It is important to instruct your patients that they should always have a backup pen available	TRUE

If you have questions or are unclear about any of these responses, please refer to the Direct HealthCare Professional Communication for Humalog® U-200 KwikPen®.

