5.7. Study size

The target sample sizes for the HCP and patient populations are 280 completed surveys for each population. The size of the sample was determined based on both practical and statistical considerations. There is no target comprehension rate specified *a priori*. A sample of 280 completed surveys for both HCPs and patients will allow estimation of the comprehension rate for each key safety message with a moderately high degree of precision. The table below shows the precision of the estimates for level of understanding using two-sided 95% CIs obtained with the sample size of 280 completed surveys. The noted CIs are used to indicate that for any survey-estimated rate of understanding, the true population rate of understanding is at least as high as the lower limit of the 95% CI and may be as high as the upper limit of the 95% CI.

Equation 1

$$95\%CI = Response\ Rate \pm 1.96 \left\{ \sqrt{\left[\frac{Response\ Rate(1-Response\ Rate)}{Sample\ Size} \right]} \right\}$$

Table 1 Sample size calculations

Sample Size	Observed Response Rate* (e.g. Knowledge)	2-Sided 95% CI		
		Half-width	Lower Limit	Upper Limit
280	50%	5.9%	44.1%	55.9%
	60%	5.7%	54.3%	65.7%
	70%	5.4%	64.6%	75.4%
	80%	4.7%	75.3%	84.7%
	90%	3.5%	86.5%	93.5%

*Percentage of responders who correctly answered a question.

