5.9. Data analysis

Data collected from the survey will be reported as descriptive statistics. Frequency distributions with 95% CIs will be calculated for respondent responses to all questions that address the survey objectives. Responses to each question relating to the key safety messages will be categorized as “Correct response” and “Incorrect response”. “I don’t know” is categorized as an incorrect response unless otherwise specified.

In addition to the overall analysis, survey data will be analyzed to determine if there are any differences for HCPs, by medical specialty.

The following will be reported as part of the analysis:

HCPs:

Survey administration

- The number of survey invitations issued by method of distribution and specialty

- The number of survey invitations returned due to incorrect mailing address of HCPs invited to participate in the survey
- The number of HCPs who responded to the invitation to participate in the survey
- The number of HCPs eligible for participation in the survey
- The number of ineligible HCPs along with the reasons for ineligibility
- The number of eligible HCPs who completed the survey

Demographic characteristics of participants

- Distribution of participants by age groups
- Distribution of participants by gender
- Distribution of participants by practice setting
- Distribution of HCP by state
- Distribution of participants by medical specialty
- Distribution of participants by years in medical practice
- Distribution of participants by number of patients treated with Humalog U-200 KwikPen

Responses to questions pertaining to the survey objectives:

- Awareness of the DHPC on the correct use of Humalog U-200 KwikPen
- Understanding of the key safety messages
- Self-reported practices with respect to communication of the key safety messages in clinical practice

Patients:

Survey administration

- The number of invitations distributed
- The number of survey invitations returned due to incorrect mailing address of patients invited to participate in the survey
- The number of patients who responded to the invitation to participate in the survey
- The number of patients eligible for participation in the survey
- The number of ineligible patients along with the reasons for ineligibility
- The number of eligible patients who completed the survey

Demographic characteristics of participants

- Distribution of participants by age groups
- Distribution of participants by gender
- Distribution of patient by state

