5.11. Limitations of the research methods

The participants will be self-selected since they will voluntarily respond to the invitation to participate. The survey recruitment strategies will include a random sample of HCPs who received educational outreach, which should be generalizable to the overall HCP population who are educated about the use of Humalog U-200 KwikPen.

Patients will be recruited via the PBM database and will be identified as those patients who have filled/refilled a prescription for Humalog U-200 KwikPen.

Additionally, inherent in survey research is the reliance on the respondent's recall for whether or not the risk minimization communication was received in order to evaluate the scope of risk minimization measures. If the respondent says she/he did not receive the communication, the risk minimization program is evaluated as not optimally disseminating material. It is possible, however, that respondents may simply not recall receiving the tools that were, in fact, received. It is also possible that they have acceptable understanding of the risks and appropriate behaviors despite not receiving or recalling receipt of the risk minimization measure-specific communication. All data from the survey are self-reported and therefore susceptible to possible reporting bias. This is also applicable to the patients' self-reporting of their practice behaviors to minimize the risks. There may be discrepancies between what respondents report about their practices and their actual behaviors.

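### The HCP questionnaire caps zero-patient respondents at 140 of 280, while the protocol body treats the completers as a random, generalizable sample and never mentions the cap

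*Protocol*

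**What the plan says.** **Questionnaire (Appendix I.1).** Question 11 asks "For how many patients have you prescribed, or managed their treatment with, Humalog® U-200 KwikPen". An answer of 0 carries the programmer instruction "TERMINATE AFTER QUESTION 14 IF 140 OR MORE COMPLETE RESPONDENTS HAVE ANSWERED 0, WHERE 140 IS A CONFIGURABLE NUMBER". The two items on discussing safe use and the patient letter with patients are withheld from the same group. For the first of them the instruction is "DO NOT DISPLAY QUESTION 20 IF 0 IS SELECTED IN QUESTION 11", and Question 21 has the matching one.

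**Sampling and generalization.** Section 4 says that testing a representative population allows generalization. Section 5.4 describes a random sample from the list of HCPs who were sent the DHPC. Section 5.11 says of this sample "which should be generalizable to the overall HCP population who are educated about the use of Humalog U-200 KwikPen". Section 5.2 mentions a mix of HCPs who have and have not prescribed the product, but gives no proportion and no quota.

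**Size and precision.** Section 5.7 states "The target sample sizes for the HCP and patient populations are 280 completed surveys for each population". It says that this number "will allow estimation of the comprehension rate for each key safety message with a moderately high degree of precision", and it reads the confidence interval as bounding the true population rate.

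**Analysis.** Section 5.9 says "In addition to the overall analysis, survey data will be analyzed to determine if there are any differences for HCPs, by medical specialty". No split by Question 11 is named. The number of eligible HCPs, the number of ineligible HCPs with reasons, and the distribution by number of treated patients are to be reported. Section 6.2 limits the analysis to completed surveys.

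**The concern.** A random sample that stops taking one kind of eligible respondent at a fixed count becomes a quota sample in that respect. If the cap is reached, the 280 completers split 140 to 140 by design, whatever the split among eligible DHPC recipients. HCPs who have used the product may well know the safety messages better than those who have not. An unweighted overall rate would then depend partly on the cap, and its confidence interval would be centred on a different quantity from the population rate named in Section 5.7. Section 5.3 judges effectiveness by whether a majority of respondents are aware of the messages, so the level of the rate matters even without a hypothesis test.

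The protocol also contradicts itself on eligibility. The cap is neither an inclusion nor an exclusion criterion, yet the termination text in the survey legend tells the respondent they are not eligible. Section 5.9 does not say whether such an HCP counts as eligible or ineligible.

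Lastly, the discussion endpoint has a smaller denominator than the one for which precision is given.

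**Working it through.** **Inputs from the Protocol.** Target n = 280 and Equation 1 (Section 5.7); cap = 140, skip rules for Questions 20 and 21 (Appendix I.1).

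**Inputs assumed, because the documents do not give them.** w is the share of eligible respondents who would answer 0. pU and pN are the proportions correct with and without at least one U-200 patient.

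**1. Reproduce Table 1.** Half-width = 1.96 × √(p(1 − p)/280). At p = 50, 60, 70, 80, 90% this gives 5.86, 5.74, 5.37, 4.69, 3.51 points, which agrees with the stated 5.9, 5.7, 5.4, 4.7, 3.5.

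**2. Questions 20 and 21 when the cap is reached.** n = 280 − 140 = 140. The same formula gives:

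| Observed rate | n = 280 (Table 1) | n = 140 |
|---|---|---|
| 50% | 5.9 | 8.3 |
| 60% | 5.7 | 8.1 |
| 70% | 5.4 | 7.6 |
| 80% | 4.7 | 6.6 |
| 90% | 3.5 | 5.0 |

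The ratio is √2 = 1.41. Because the cap is configurable, the denominator moves with it. An assumed cap of 70, if reached, leaves n = 210 (6.8 points at 50%); an assumed cap of 210 leaves n = 70 (11.7 points).

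**3. Shift in the overall comprehension rate.** The population rate is w·pN + (1 − w)·pU. With 280 completers, the zero-patient share of the sample is s = min(w, 0.5), so the sample rate is s·pN + (1 − s)·pU. The shift is therefore (w − 0.5)(pU − pN) when w > 0.5, and zero otherwise.

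| pU / pN (assumed) | w ≤ 50% | w = 70% | w = 80% | w = 90% |
|---|---|---|---|---|
| 85% / 60% | 0 | +5.0 | +7.5 | +10.0 |
| 90% / 70% | 0 | +4.0 | +6.0 | +8.0 |
| 90% / 80% | 0 | +2.0 | +3.0 | +4.0 |

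In the first row, when the cap binds, the sample rate is 0.5 × 85 + 0.5 × 60 = 72.5%. The population rate is 67.5, 65.0 or 62.5% at w = 70, 80 or 90%. The pooled half-width at 72.5% is 1.96 × √(0.725 × 0.275/280) = 5.2 points.

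**4. Precision after weighting.** With 140 in each stratum and known weights, the half-width is 1.96 × √([w²·pN(1 − pN) + (1 − w)²·pU(1 − pU)]/140). For 85%/60% and w = 80%: 1.96 × √([0.64 × 0.24 + 0.04 × 0.1275]/140) = 1.96 × √(0.1587/140) = 6.6 points.

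**The case against.** The case on the other side is substantial, and much of it stands.

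- A reader might infer that the overall HCP rate is biased. The documents do not support that. The shift needs both a zero-patient share above 50% and a knowledge gap, and neither is given. Eligibility already requires awareness of the product, and the DHPC is aimed at likely prescribers as well as pharmacists, so a share of 50% or less cannot be excluded.
- A reader might infer that Table 1 is wrong. It is not. Section 5.7 offers it "for level of understanding using two-sided 95% CIs obtained with the sample size of 280 completed surveys", and every completer answers the comprehension items in Question 15.
- A reader might infer that the cap or the skip harms the discussion endpoint. The skip is sensible, since an HCP with no U-200 patients has no such discussions to report. At its stated value the cap protects the denominator. Without it, a zero-patient share of 70 to 90% would leave 280 × 0.30 = 84 down to 280 × 0.10 = 28 answers, with half-widths of 10.7 to 18.5 points at 50%.
- A reader might infer that the cap will be changed during fieldwork. The text says only that the number is configurable, not when or by whom.
- The study is descriptive, and Section 5.10 refers to an analysis plan that is not at hand. Weighting or further table splits may be set out there. In the 85%/60% illustration the population and sample rates are all majorities, so the reading under Section 5.3 would not change.

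What remains is within the protocol itself. The body asserts a random, generalizable sample, the questionnaire applies an unmentioned quota, and eligible HCPs can be turned away as ineligible. An analysis plan would not reconcile those statements. Nor is the majority reading always safe: with assumed rates of 70% and 40% and w = 80%, the population rate is 0.8 × 40 + 0.2 × 70 = 46%, while the capped sample gives 55%.

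**Conclusion.** The point holds as an inconsistency with a conditional consequence. Certain from the text: the cap exists, it is missing from the sections on population, criteria, study size, analysis and limitations, and it conflicts with the eligibility criteria. Conditional: if more than half of eligible respondents would answer 0 and the groups differ in knowledge, an unweighted overall comprehension rate is shifted by (w − 0.5) times the gap. That is +5 to +10 points at 85% versus 60% correct and a 70 to 90% zero-patient share, +2 to +4 with a 10-point gap (90% versus 80%), and zero at a share of 50% or less. For Questions 20 and 21, n is 140 if 280 surveys are completed and the cap is reached at 140; the half-width is then 8.3 points at 50%, and the protocol states no precision for these items. The quota is a legitimate choice. The weakness is that it is not disclosed and not carried into the description of the estimate. The correction is cheap and worth making before launch.

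**What to change.** 1. State the cap and its purpose in Sections 5.2 and 5.7, and fix its value before launch.
2. In Section 5.9, count HCPs ended by the quota as a separate category from ineligible HCPs, and reconcile the termination text with Sections 5.4.1 and 5.4.2.
3. Report HCP comprehension separately for Question 11 = 0 and Question 11 ≥ 1, each with its own 95% confidence interval.
4. If the cap binds, weight the overall rate by the Question 11 shares among all screened-eligible HCPs, including those ended over quota. Termination comes after Question 14, so their answers on product experience and the employment exclusion are already given. Section 6.2 needs an exception so that these screening answers can be used for the weights.
5. Add an n = 140 precision row for Questions 20 and 21.
6. Mention the quota in Section 5.11.

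**Cost.** No new data collection: some wording and one extra table split. If the cap does not bind, the overall estimate stays as it is. If it binds, the overall interval widens, for example from about 5.2 to 6.6 points at 85%/60% correct with an 80/20 mix, before allowing for uncertainty in the weights.
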